### *Medical Assessment*

Study participants will be asked about their medical history and current medication use. Anthropometric measures (e.g. height and weight) and vital signs such as blood pressure and heart rate will be assessed as part of the inclusion/exclusion criteria assessment. A complete physical examination will be performed during this time.

If an ECG for the patients has been taken within one month of enrolment, these patients do not require a repeat ECG reading at the Screening Visit and results will be recorded accordingly. Monitoring of vitals will also be performed at baseline and prior to each in person follow-up visit to provide close monitoring for patient safety.

## **Baseline Visit**

### *Biological Samples*

Blood samples may be drawn at baseline and at the 3-month and 12-month visits. The timeframe for blood draw results will be based on institutional requirements and left at the discretion of the treating physician. In addition, blood samples to assess for the presence of biomarkers of fibrosis, inflammation, and cardiovascular disease will be recorded at these visits. These include NT pro-BNP, soluble ST2, and C-reactive protein and Galectin-3.

All blood samples will be processed at the trials' local sites, and the results will be entered onto the electronic database capture platform, DACIMA (Software Inc), after each visit. Blood samples will not be shipped or stored after processing.

List of Study Labs	
Panel:	Specific Tests:
Liver Panel	ALT, AST, ALP, and GGT
Renal Panel	Creatinine, BUN/Cr, GFR
Cholesterol Panel	Total cholesterol, HDL, LDL, and Triglycerides
Basic Panel	HbA1c, CBC, BMP
Coagulation Panel	PT/INR, PTT
Inflammation/Fibrosis/CVD Biomarkers	NT-ProBNP, Soluble ST2, C-RP, and Galectin-3

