#### **7) Study Participant Safety**

Study participants will be evaluated at multiple timepoints across the study: their in-person 3-month and 12-month visits and their 6, 9 and 13-month phone calls. This evaluation includes any adverse events, especially adverse events (AEs) related to AAD treatment. AEs related to dronedarone are defined in the **Safety/Adverse Event Monitoring Plan** section of this protocol.

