### ***b) Dronedarone***

Antiarrhythmic drugs such as, dronedarone can be prescribed as standard of care. They too carry adverse effects which include; pulmonary events (cough, dyspnea, pulmonary toxicity), thyroid toxicity (hypo- or hyperthyroidism), hepatic toxicity, bradycardia <50bpm, QT-interval prolongation, gastrointestinal events (loss of appetite, nausea, vomiting, abdominal pain and diarrhea), neurological events (dizziness, headache, asthenia, peripheral neuropathy), chest pain or discomfort, heart failure, decompensation in patients with heart failure, and an increase in serum creatinine.

Although a black box warning has been issued by the FDA, dronedarone's associated risk of death and stroke is based on patients with heart failure, decompensated heart failure, or permanent atrial fibrillation. These classes of patients fall into the exclusion criteria and thus, will not be enrolled in this trial. Dronedarone is also contraindicated in AF patients who cannot be cardioverted into normal sinus rhythm.

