### *Follow-up of SAEs, Unexpected Events, and Related Events*

Any SAEs that are unresolved at the time of the patient's termination from the trial will be followed by the clinical investigator until the events have been resolved, the patient is lost to follow-up, or the adverse event is otherwise explained or has stabilized.

For the safety and adverse events monitoring data, incidents of adverse events will be summarized by event type, grade, and body system. The proportion of patients with AEs will be calculated and presented with a 95% confidence interval.

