## **5.5 Liver Injury**

Hepatocellular liver injury, including acute liver failure requiring transplant, has been reported in patients treated with MULTAQ in the post marketing setting. Advise patients treated with MULTAQ to report immediately symptoms suggesting hepatic injury (such as anorexia, nausea, vomiting, fever, malaise, fatigue, right upper quadrant pain, jaundice, dark urine, or itching). Consider obtaining periodic hepatic serum enzymes, especially during the first 6 months of treatment, but it is not known whether routine periodic monitoring of serum enzymes will prevent the development of severe liver injury. If hepatic injury is suspected, promptly discontinue MULTAQ and test serum enzymes, aspartate aminotransferase (AST), alanine aminotransferase (ALT) and alkaline phosphatase, as well as serum bilirubin, to establish whether there is liver injury. If liver injury is found, institute appropriate treatment and investigate the probable cause. Do not restart MULTAQ in patients without another explanation for the observed liver injury.

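### The study laboratory list schedules no thyroid test and no bilirubin, so asymptomatic thyroid dysfunction surfaces only through local testing and liver enzyme rises cannot be uniformly classified.

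*Combined protocol and SAP*

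**What the plan says.** Safety is the seventh secondary endpoint. It covers any adverse event, "especially adverse events (AEs) related to AAD treatment", and refers the reader to a safety monitoring plan section for the dronedarone-related events. No section carries that exact title. The matching text is the Dronedarone subsection under adverse events related to the trial, which names "thyroid toxicity (hypo- or hyperthyroidism), hepatic toxicity, bradycardia <50bpm, QT-interval prolongation" among other effects.

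The List of Study Labs, under Biological Samples, itemises six panels. The liver panel is "ALT, AST, ALP, and GGT". The others are renal, cholesterol, basic (HbA1c, CBC, BMP), coagulation and four biomarkers. None contains a thyroid test, and bilirubin is not listed. On timing, the section says "Blood samples may be drawn at baseline and at the 3-month and 12-month visits". It also says that samples are processed locally and not kept afterwards.

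Appendix C, section 5.5, opens its work-up with a condition: "If hepatic injury is suspected, promptly discontinue MULTAQ and test serum enzymes". It then names AST, ALT and alkaline phosphatase "as well as serum bilirubin, to establish whether there is liver injury".

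For reporting, the section on follow-up of SAEs states: "The proportion of patients with AEs will be calculated and presented with a 95% confidence interval".

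**The concern.** The plan makes drug-related harm the focus of its safety endpoint, names thyroid and hepatic toxicity, and already schedules blood at three visits. The tests on that blood include lipids, HbA1c and four biomarkers. They omit any thyroid assay, and they omit bilirubin, which the insert uses to complete the picture of suspected liver injury.

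What is at stake is how the safety table can be read. A thyroid abnormality without symptoms enters the table only if someone orders a test outside the protocol. The Blinding section says that site investigators cannot be blinded, so the decision to order that test can depend on the arm. A low or equal count of thyroid events in the two arms would then mix true frequency with the frequency of testing. For the liver, an isolated enzyme rise could not be told apart, on a common basis across sites, from one with raised bilirubin.

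**Working it through.** The plan states no figure to reproduce. The check sets the sections side by side.

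1. **Thyroid.** Named as a harm in the Dronedarone subsection. Tests in the List of Study Labs: 0. Tests in the visit lists of the Study Schedule or in the Schedule of Events: 0. Scheduled draws carrying a thyroid test: 0 of 3.

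2. **Liver.** Appendix C, section 5.5, names four tests for suspected injury: AST, ALT, alkaline phosphatase and bilirubin. The List of Study Labs has the first three, plus GGT. Coverage is 3 of 4, with bilirubin missing. Two assumptions apply. The BMP is not itemised and is taken not to include bilirubin. The hepatic panel named in the baseline and 3-month visit lists is taken to be the four-test panel defined under Biological Samples.

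3. **Is bilirubin collected by another route?** The insert ties it to suspicion. The protocol body has no work-up for suspected liver injury that carries this over, so the study procedures do not call for bilirubin either routinely or on suspicion.

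4. **Can a later abnormality be classed as new?** The adverse event data collection section compares later laboratory abnormalities with those present at randomization. Patients may enter with or without earlier antiarrhythmic treatment (Inclusion Criteria, item 2), and the Dronedarone subsection attributes thyroid toxicity to antiarrhythmic drugs in general. Prior amiodarone toxicity excludes a patient only if it affected liver or lung (Exclusion Criteria, item 10). A patient could therefore enter with an unmeasured thyroid abnormality. As no sample is kept, the baseline value cannot be obtained later.

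5. **Are the draws themselves secure?** The wording under Biological Samples is permissive. The Study Schedule names creatinine, hepatic panel and biomarkers at baseline and 3 months, but only biomarkers at 12 months. The 12-Month Visit text under Study Procedures calls that visit the same as the 3-month visit, and the Schedule of Events marks a blood draw at all three. Even the four listed liver enzymes are not clearly required at 12 months.

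6. **How would a zero count read?** Suppose no thyroid event were reported among the 165 patients of an arm. The exact two-sided 95% upper limit is 1 − 0.025^(1/165) = 2.2%. With the planned 20% loss, 165 × 0.80 = 132 patients, and the limit is 1 − 0.025^(1/132) = 2.8%. These limits are valid for reported events. They do not bound the rate of biochemical thyroid dysfunction, because no scheduled test looks for it.

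**The case against.** A reader might infer that the safety endpoint cannot detect these harms at all. The documents do not support that. ALT, AST, ALP and GGT are listed, so hepatic toxicity is detectable. The endpoint takes in any adverse event at visits and calls, clinically significant results drawn during the trial count as adverse events with no restriction to the study list, and sites may schedule extra visits. Clinically apparent thyroid or liver disease would be recorded.

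A reader might also infer that leaving bilirubin off a routine list contradicts the insert. It does not: the insert asks for bilirubin once injury is suspected, and for routine use it only suggests considering periodic enzymes.

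Further points are fair. Thyroid toxicity appears once, in a sentence about antiarrhythmic drugs in general, and the abbreviated insert does not mention it. The same sentence names pulmonary toxicity and peripheral neuropathy, which have no scheduled test either, and the protocol adopts no rule that each named harm needs one. Some sites may report bilirubin or thyroid results from local practice. Secondary endpoints are descriptive only.

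These points limit the claim without removing it. A result exists only if a test is drawn, and here unscheduled testing is ordered by people who know the arm. Secondary endpoints are still to be compared between arms, and a descriptive comparison needs the same measurement in both. Site-dependent bilirubin is itself non-uniform. Unlike lung or nerve effects, these two gaps can be closed with blood the plan already schedules.

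**Conclusion.** The concern holds in a limited form. The protocol schedules no thyroid test and no bilirubin at any of its three draws. Asymptomatic thyroid dysfunction would therefore depend on local testing that may differ by arm, with no scheduled baseline value, and enzyme rises could not be uniformly classified by concurrent bilirubin.

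The number of patients affected cannot be estimated, because the documents give no rate of thyroid or liver abnormality and no rate of local testing. The conclusion rests on the two readings of the BMP and the hepatic panel stated above. If the hepatic panel is meant to include bilirubin, the liver part becomes a matter of making the sections agree, and the thyroid part is unchanged.

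This is an inexpensive improvement in safety ascertainment. It has no bearing on sample size, power or either co-primary analysis.

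**What to change.** - Add total bilirubin to the liver panel and add TSH to the List of Study Labs, at the existing baseline, 3-month and 12-month draws, in both arms.
- Reconcile the permissive wording under Biological Samples, the 12-Month Visit text, the three visit lists in the Study Schedule and the Schedule of Events, so that the same panel is drawn at all three visits. Without this, adding analytes does not secure the data.
- Correct the cross-reference in the safety endpoint so that it points to an existing section.
- Tabulate by arm the patients with out-of-range values, and those with an enzyme rise together with raised bilirubin. Count thyroid abnormalities as new only where the baseline value was in range.

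This is data collection for the safety endpoint only. No management threshold or treatment rule is proposed.

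The cost is two extra assays at three visits, two data-capture fields, one table, and a protocol amendment with IRB approval. No new visit, procedure or staff is needed. Patients already enrolled would lack baseline values, since samples are not stored, and should be shown separately in the table.

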### ***Health Survey Administration***

#### ***AFEQT Questionnaire***

The AF Effect on QualiTy of life survey (AFEQT) is a questionnaire form that measures the patients' perceptions of their symptoms, functional impairments, treatment concerns, and overall satisfaction with their treatment. This questionnaire assesses 20 items categorized under 4 domains (symptoms, daily activities, treatment concern, treatment satisfaction). AFEQT has also been validated by comparison of mean scores too per clinicians' assessments. It has good convergent and divergent correlations with other well-established questionnaires (SF-36, EQ-5D SCL, AFSS, and GAD-7). Patients will be required to fill out this paper questionnaire at their baseline, 3-month and 12-month visits.

#### ***AFSS Questionnaire***

The Atrial Fibrillation Severity Scale (AFSS) is a questionnaire form that measures burden of AF if present. The AF symptom burden score is derived from the AFSS summary score that averages the frequency, duration, and patient perceived severity of AF episodes. A higher score indicates greater AF burden. Patients will be required to fill out this 6-item paper questionnaire at their baseline, 3-month and 12-month visits.

### ***Cardiac Magnetic Imaging (CMR)***

#### ***CMR Protocol***

All patients will undergo a CMR scan +/- 90 days (preferably within 30 days) prior to ablation using the CMR protocol (***MRI Sequence and Image Processing Software, Appendix B***). The purpose of the initial MRI is to quantify the degree of atrial structural remodeling or fibrosis prior to ablation. Patients are screened for metal fragments. If metal fragments are identified, the MRI team will scan the participant on a 1.5T scanner. If metal fragments are not identified, the MRI team will scan the participant on a 3T scanner. If a patient has a heart rate  $\geq 90$  beats per minute, they will be pre-medicated with a beta blocker prior to the MRI to obtain optimal images.

The patient will be injected with gadolinium (Gadovist, Class II macrocyclic gadolinium, low risk) or a similar agent, contrast enhancement. A brief period of time is taken to allow gadolinium to perfuse the tissues and wash-out to appropriate concentrations in the heart. The patient will then undergo CMR sequencing, which lasts approximately 20-25 minutes. Throughout the procedure, the patient is monitored for adverse reactions to the contrast. If the patient develops any contraindications listed in the

Page 22 of 49

Version 4.0:  
Revision Date: April 27th, 2022

Copyright© April 2022 Tulane University School of Medicine, Academic Research Organization on behalf of the Principal Investigator.  
All rights reserved.

TULANE UNIVERSITY  
Academic Research Organization

exclusion criteria prior to their follow-up scans, the patient will be excluded from receiving subsequent CMRs.

Atrial fibrosis progression will be compared and contrasted from the patient's baseline image to their follow-up CMR scans at 3 months and 1-year post-ablation. A pregnancy test will be performed at baseline and before every CMR scan during each study visit in pre-menopausal women. If a patient becomes pregnant during the trial (after baseline CMR scan), the patient will not be allowed to undergo any follow up CMR scans until 10 days post-partum.

All CMR images will be uploaded to Marrek, Inc., (Salt Lake City, UT) Merisight portal as they arrive from each clinical trial site. If the imaging specialist believes the baseline image does not meet quality standards, they will not be further processed. Therefore, the patient will be excluded from the EDORA trial. CMR scans will be uploaded onto the Merisight portal. Any reports in addition to the CMR scanned images will help to aid in Marrek's calculations and analysis.

Marrek, Inc., will analyze and process the images, verifying that the patient has a proportion of atrial fibrosis (not limited to advanced stage fibrosis). Utah Stages 1-4 will be used to classify patients based on the percentage of fibrosis. Access to Merisight will also be granted to additional analysts who will separately determine LA and LV function and strain and aid in MRI sequencing.

A final report from Marrek Inc. will be uploaded onto Merisight's portal and uploaded onto DACIMA. All CMR scans will maintain identifying information to allow trial sites to verify that returned reports match the patients submitted identified information.

Baseline, 3 months, and 1-year CMR scans for 330 study participants will be pulled from Phillips IntelliSpace Picture Archiving and Communication System (PACS) and stored on DACIMA. All segmentations and images will also be stored on our encrypted server.

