## **FOR FEMALE PATIENTS ONLY:**

1. Pre-menopausal (last menstruation  $\leq$  1 year prior to screening visit) who:
  - a. Are pregnant or breast-feeding or plan to become pregnant during the study period or,
  - b. Are not surgically sterile or,
  - c. Are of childbearing potential and are unwilling to practice two acceptable methods of birth control or,
  - d. Do not plan to continue practicing two acceptable methods of birth control throughout the trial (highly effective methods of birth control are defined as those, used alone or in combination, that result in a low failure rate i.e. less than 1% per year when used consistently and correctly).

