### **Day of Cardiac Ablation**

After the baseline visit, patients will be scheduled for a cardiac ablation. Clinical investigators will schedule ablation procedures within 90days after CMR imaging has been completed.

Patients will be medically assessed by the site investigator. Patients who are deemed by the site investigator to have not tolerated the ablation well will not be enrolled in the study. Due to current hospital SOC, patients may be discharged up to 24 hours after ablation. Discharge may be expedited per physician discretion and other hospital-based policies (e.g. COVID-19, etc.).

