### *Dosing and IMP Administration*

Drug/placebo therapy starts the same day after the ablation procedure. A 3-month supply will be provided to all participants. Dronedarone 400mg or an oral placebo tablet will be administered twice daily (morning and evening) along with substantial meals. No dosing adjustment is needed in cases of mild renal impairment. Any adjustment to treatment would be considered a secondary endpoint and will not prompt an interruption in subsequent follow-up visits and assessments. Study participants will continue to be followed for primary and other secondary endpoints.

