### **Baseline CMR Visit (Day -90 to 0)**

- Verify inclusion/exclusion criteria.
- Document study eligibility has been verified by site investigator signature.
- Confirm medication/ concomitant therapy.
- Collect weight and vital signs.
- Obtain baseline CMR scan.
- Blood draw to obtain baseline creatinine levels, hepatic panel as well as biomarkers for fibrosis and inflammation.
- Obtain baseline AFEQT online questionnaire.
- Obtain baseline AFSS online questionnaire.
- Determine that the baseline scan meets standard requirements for enrollment.

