## ***Risks Associated with Gadolinium Contrast in CMR***

Page 30 of 49

Version 4.0:  
Revision Date: April 27th, 2022

Copyright© April 2022 Tulane University School of Medicine, Academic Research Organization on behalf of the Principal Investigator.  
All rights reserved.

TULANE UNIVERSITY  
Academic Research Organization

Risks associated with gadolinium include:

- Discomfort, tingling, warmth of the lips, metallic taste in the mouth, nausea, or headaches. This risk is small (1 in 100 people) and in most instances these symptoms disappear very quickly.
- Type 1 hypersensitivity reaction. Clinical staff will stop its use immediately and will provide antihistamine medication or epinephrine, depending on the severity of the reaction. Severe reactions rarely occur, < 1 in 300,000 people.
- Approximately 4% of patients with severe kidney disease receiving gadolinium based contrasting agents are at a higher risk of developing Nephrogenic Systemic Fibrosis (NSF). Although rare, this disease can be serious, causing skin thickening (fibrosis) as well as thickening in other organs of the body such as, the brain, heart and bone and can even cause death. NSF has also been reported in those who have had recent major surgery, infection or have cancer.  
There have been no reports of NSF in patients receiving gadolinium who have normal kidney function. (Patients with acute or chronic severe kidney disease or with a low glomerular filtration rate (GFR), <30 mL per minute per 1.73 m^2 will be excluded from the EDORA trial).
- A pregnancy test will be conducted before each CMR scan as gadolinium may cause harm to the fetus. (Any pregnant patients at the time of enrollment will be excluded from the trial).

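### No pregnancy test is scheduled on Day 0, so for pre-menopausal women the last one may be up to 90 days old when a Category X drug is started

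*Combined protocol and SAP*

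**What the plan says.** **Eligibility.** Under the exclusions for female patients, the first item for pre-menopausal women is "Are pregnant or breast-feeding or plan to become pregnant during the study period or". Further items, each joined by an or, exclude women who are not surgically sterile, and women of childbearing potential who will not use, or do not plan to keep using, two methods of birth control. The gadolinium risk section repeats that a patient pregnant at enrollment is excluded. The Randomization section limits randomization to patients who meet the criteria.

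**Testing.** Pregnancy tests are mentioned in two places. The CMR Protocol section says: "A pregnancy test will be performed at baseline and before every CMR scan during each study visit in pre-menopausal women". The gadolinium risk section gives the reason: "A pregnancy test will be conducted before each CMR scan as gadolinium may cause harm to the fetus".

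**Timing.** The Study Schedule places the baseline CMR visit at Day -90 to 0, and its list includes "Verify inclusion/exclusion criteria". The Day of Cardiac Ablation section says: "Clinical investigators will schedule ablation procedures within 90days after CMR imaging has been completed". The CMR Protocol section prefers a scan inside 30 days. On product, Dosing and IMP Administration says: "Drug/placebo therapy starts the same day after the ablation procedure".

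**Day 0.** The Day of Cardiac Ablation section also says: "Patients will be medically assessed by the site investigator". The Schedule of Events adds a review of history and medications. No pregnancy test appears in the Day 0 list, in the List of Study Labs or in any row of the Schedule of Events.

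**Drug.** Appendix C, section 4, lists dronedarone as Pregnancy Category X and contraindicated in pregnancy.

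**Pregnancy during the trial.** The CMR Protocol section says that "the patient will not be allowed to undergo any follow up CMR scans until 10 days post-partum". It does not mention trial product.

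**The concern.** The tests follow the contrast agent, given at three scans, and not the drug, taken twice daily for a year. Non-pregnancy is a condition of randomization, but the only scheduled test that can confirm it may predate randomization by up to three months. The medical assessment and history review on Day 0 can bring out a pregnancy that the woman already knows about. They cannot bring out one that she does not know about.

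What is at stake is fetal exposure to a contraindicated drug from the first dose, undetected until the 3-month scan. A secondary cost is that a woman randomized while pregnant would stay in the intention-to-treat set although she was ineligible.

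**Working it through.** The plan states no figure on this point. The check is interval arithmetic on its visit windows, followed by an illustration of scale.

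**Inputs from the protocol**
- Baseline CMR visit, with test: Day -90 to Day 0 (Study Schedule), with a preference for 30 days or less before ablation (CMR Protocol).
- First dose: Day 0 (Dosing and IMP Administration).
- 3-month visit, with scan and test: Day 90 ± 30, so Day 60 to 120.
- 12-month visit, with scan and test: Day 365 ± 30, so Day 335 to 395.

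**Intervals as planned**
- Last test to first dose: 0 − (−90) = 90 days at most, 0 at least; 30 or less if the preference is met.
- Dosing before the first on-drug test: nominally 90 days, range 60 to 120.
- Baseline test to 3-month test: at most 90 + 120 = 210 days. With a Day -30 scan and a Day 90 visit it is 30 + 90 = 120 days.
- 3-month test to 12-month test: nominally 365 − 90 = 275 days, at most 395 − 60 = 335 days.

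The CMR Scan entry in the adverse event section treats 90 days as only a preference for the first scan. The Study Schedule and the Day of Cardiac Ablation section both set 90 days as the limit, so 90 is used here.

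**Intervals with a Day 0 test**
- Last test to first dose: 0 days.
- Longest gap from the last pre-dose test to the 3-month test: 120 days instead of 210.

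**Scale (illustration only).** The documents do not give the number of pre-menopausal participants. Assume 10 to 30. Assume conception at 1% per year, the bound the female criteria attach to highly effective methods used consistently and correctly. Expected conceptions = gap/365 × 0.01 × N.

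| Gap | N = 10 | N = 30 | Dronedarone arm (half, by 1:1 allocation) |
|---|---|---|---|
| 90 days | 90/365 × 0.01 × 10 = 0.025 | 90/365 × 0.01 × 30 = 0.074 | 0.012 to 0.037 |
| 30 days | 30/365 × 0.01 × 10 = 0.008 | 30/365 × 0.01 × 30 = 0.025 | 0.004 to 0.012 |

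**Who can be at risk.** Read literally, the item on surgical sterility removes almost every pre-menopausal woman able to conceive. But the two contraception items would then have almost no one to apply to, and neither would the CMR section's pre-scan tests and its rule for a pregnancy during the trial. Read together, these passages imply that such women are expected to enrol.

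**The case against.** **The eligibility rules already cover it.** The protocol excludes pregnant women twice and randomizes only eligible patients, and enrollment is settled after ablation. Non-pregnancy is therefore a Day 0 condition. This stands: what is missing is confirmation by test, not the rule. For the same reason, a reader might infer that the plan, followed to the letter, allows a pregnant woman to be dosed. The documents do not support that. Followed to the letter, the sterility item leaves few or no such women, and the exclusions forbid randomizing one who is pregnant. The gap depends on the broader reading of the female criteria and on a pregnancy nobody has recognized.

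**Contraception is required.** Two methods are an entry condition, and Appendix C, section 5.10, requires effective contraception on drug. This stands, and it is why the expected numbers are small.

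**There is no rule to stop product.** A reader might infer that, because the on-study pregnancy rule withholds only the scan and the Treatment Groups section names only a new antiarrhythmic as a reason to stop, trial product may continue in pregnancy. The documents do not support that either. The rule sits in an imaging section. The Treatment Groups section does not call its trigger the only one. Appendix C contraindicates the drug in women who are pregnant. Site investigators are not blinded and carry primary responsibility for their patients' safety. It is true that for pregnancy arising on drug Appendix C says only to inform the patient of the hazard, whereas for some other events it says outright to discontinue. A sentence would help, but it would clarify and not correct.

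**The remedy treats the shorter exposure.** At a constant rate, a year of dosing carries about four times the conceptions of a 90-day gap (365/90 = 4.1), and the interval between the 3-month and 12-month tests is longer than the pre-dose one. This is true, and a Day 0 test does not shorten it. The Day 0 test has a narrower purpose: to confirm an existing eligibility condition before a contraindicated drug is first given.

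**Other documents or hospital practice may supply the test.** The consent pages are not in this copy, and hospitals may test before ablation anyway. The protocol text reviewed does not require it.

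**Conclusion.** The point holds as a cheap safety improvement. The only scheduled test before first dose belongs to the baseline CMR visit, up to 90 days before Day 0 (30 or less if the preference is met). No test is listed on Day 0, and the next falls at Day 60 to 120. The interval arithmetic follows directly from the visit windows.

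That a woman could be harmed rests on one reading: that non-sterile pre-menopausal women can enrol, as the contraception items and the CMR section imply. Few are likely to be affected. Under the assumed 10 to 30 women at 1% per year, a full 90-day gap corresponds to 0.012 to 0.037 conceptions in the dronedarone arm, and a 30-day gap to a third of that. These counts are assumptions, not trial data. No endpoint, power or alpha figure changes. The case for acting is that the harm is serious and the remedy simple. The conclusion covers the protocol body, the visit lists, the Schedule of Events and Appendix C.

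**What to change.** For pre-menopausal women, add a pregnancy test to the Ablation Procedure (Day 0) list, with a negative result required before randomization and first dose, and add the matching row to the Schedule of Events. Keep the existing tests before each scan.

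The cost is a short amendment and one inexpensive test per such woman, of a kind the trial already performs. Rarely, a woman will not be randomized after she has had her baseline scan.

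As a clarification in the same amendment, the CMR Protocol section could say that a positive test means stopping trial product and notifying the coordinating centre. Non-CMR follow-up would continue as the Treatment Groups section already provides after discontinuation, and scans would be postponed as now. This adds no procedure. Tests at 6 and 9 months are a separate choice and are not part of this request.
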